15. TRIAL ORGANIZATION

This study will be conducted in Edmonton through the University of Alberta. The study staff consist of:

- A research assistant (roughly support staff grade 4-6 [per University of Alberta-Non-Academic Staff Association support staff wage scales]), who will have Alberta NetCare access through Alberta Health Services.
- CDE nurses, one or more community-based practitioners with active CDE practice and experience.
- A qualitative research associate (roughly support staff grade 8) with a graduate degree and previous experience in semi-structured interviews or focus group and thematic analyses.

Study staff will be hired by the principal investigator (Division of General Internal Medicine, Department of Medicine). The Epidemiology Coordination and Research (EPICORE) Centre (Division of Cardiology, Department of Medicine – www.epicore.ualberta.ca) provide study database, secure online database access, computerized participant allocation, and statistician services.

16. DATA MANAGEMENT

Study data, including the generation and maintenance of electronic case report forms, will be managed by EPICORE. The data will be housed on EPICORE's secure servers hosted at the University of Alberta Faculty of Medicine and Dentistry. Data access is limited to authorized EPICORE and study personnel, who will be provided with unique credentials. Study personnel will use the REDCap interface to complete electronic data entry; the collected data will be accessible via encrypted virtual private network.

As an innovation, EPICORE has designed a patient portal in REDCap to enable self-completion of patient-reported outcomes. While the baseline and follow-up visits will still be in-person, participants may choose to finish filling in patient-reported outcomes from home, on their computers or smart phones.

A copy of the locked and final study data will be stored on the principal investigator's secure server. This server space is hosted by the Data Analytics and Research Core (DARC) at the University of Alberta's Faculty of Medicine and Dentistry, and is also only accessible to authorized personnel via virtual private network. This will facilitate compliance with university policies on data retention, as well as satisfy the secondary analyses and the follow-up observational study once EPICORE's services are complete.

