6. STUDY DESIGN

This trial is an investigator-initiated prospective, single-center, open-label, randomized controlled trial of isCGM with CDE education and feedback. All participants will receive standard treatment at the discretion of their physicians.

Setting

- Tertiary care ambulatory referral clinic in Alberta, Canada, with recruitment of patients from urban primary care practices.

Intervention – isCGM + CDE Education and Feedback

- *Short Term Use of isCGM* – Participants will be given three FreeStyle Libre 2 sensors during the study period. Each sensor, once worn, provides glucose measurements for 14 days. The three sensors will provide 6 weeks of isCGM. Participants will *not* be encouraged to use FreeStyle Libre 2 sensors outside of the intended study periods, but neither will they be discouraged from doing so if they choose to of their own accord. The first sensor will be initiated with the assistance of a study team member, who will also set up the Libre 2 smart phone app and link it to the study LibreView account during the baseline visit. Subsequent sensors will be participant-initiated. Should participants encounter difficulty with sensor placement, replacement sensors will be made available, and participants will be referred to their local retail pharmacist to assist with sensor initiation. A small number of FreeStyle Libre 2 Readers will be available for those with unforeseen technical difficulties. Patients using the readers will be asked to upload their data to LibreView online via USB adapter connection to their computers, on a weekly basis.

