- *No specific monitoring of glucose* – Participants will be discouraged from accessing FreeStyle Libre 2 glucometers or other CGM during the study period. They will be free to use capillary blood glucose monitoring according to their own interest and motivation, or as directed by the CDE nurse. Advice and handouts will be provided to isCGM participants on recognizing and managing hypoglycemia.
- *Alberta Health Services Diabetes Education Group Classes* – Participants will be referred to Alberta Health Service's standard diabetes education group classes and advised to register according to their interest and motivation.
- *CDE Education and Feedback* – A CDE nurse will assess the participant. The CDE nurse will provide general diabetes education, and individualized recommendations on lifestyle (diet and physical activity) changes to improve glycemic control. Two encounters will take place with the CDE nurse. The first will occur during weeks 1-2, and the second during weeks 5-6. CDE nurses will provide education and advice according to their usual training and practices. CDE encounters will take place either in-person, or virtually, over Zoom.

Study period – The trial period will be 12 weeks. From 12 weeks onwards, select participants will be approached to participate in semi-structured qualitative interviews. Linkage of participant information to Alberta administrative health care data may occur up to 3 years after trial completion to allow examination of diabetes outcomes on an observational basis up to 52 weeks from randomization.

Blinding

- This trial is open-label. Neither patients, investigators, nor statistical analysts will be blinded to treatment allocation.

Post-Trial Observational Follow-Up – Patients will be reviewed on NetCare for laboratory values and health care utilization at 24 and 52 weeks following randomization. NetCare data accrued up to 64 weeks post-randomization will be reviewed to identify nearest lab values for the 52-week time point.

Post-Trial Qualitative Study of Experiences Using isCGM – Consenting patients and providers will be contacted after the 12 week study period to participate in semi-structured interviews exploring their experiences using isCGM or managing their blood glucose without isCGM.

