7. STUDY POPULATION

Adults (age ≥ 18 years) with type 2 diabetes and uncontrolled blood sugars, defined as HbA1c $> 7.0\%$, not on insulin therapy.

Inclusion Criteria:

1. Age ≥ 18 years with type 2 diabetes.
2. HbA1c $> 7.0\%$ within the last 6 months.
3. Non-insulin therapy.
4. Able to attend two in-person study visits.
5. English-speaking.
6. Community-dwelling
7. In possession of a cell phone capable of accessing the internet and receiving FreeStyle Libre 2 sensor readings
8. Has a primary care provider who has been in contact with the patient for diabetes in the last 12 months.

Exclusion Criteria:

1. Type 1 diabetes or diabetes clearly identified as having monogenetic etiology (e.g.: MODY).
2. Steroid-induced diabetes if steroid use is on-going or most recently taken within the last 3 months.
3. Pregnancy; plans to become pregnant within 6 months; breast-feeding.
4. Any use of insulin in the previous year.
5. Current or previous use of isCGM or rtCGM.
6. Cognitive dysfunction (SPMSQ score ≥ 5).
7. Symptoms of acute metabolic decompensation (extreme thirst, high urinary output, and weight loss, accompanied by acute fatigue or dyspnea).
8. Any terminal condition that would limit life expectancy to < 1 year.
9. Inability to use isCGM (e.g.: afraid of the device).
10. Inability to be reached by telephone.
11. Concurrent participation in another diabetes-related trial.
12. Has not already received two doses of a Health Canada-approved vaccine against SARS-CoV-2.

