9. PARTICIPANT CONSENT

Following a screening phone call, eligible patients will attend a baseline visit to complete consent for participation and randomization, as well as completion of baseline measures. For the initial screening, verbal consent (Appendix 3.1) will be obtained from potential study participants to access their provincial NetCare electronic medical records and confirm that they meet the HbA1c inclusion criteria.

A study investigator or research assistant will review the nature of the clinical trial, and the anticipated risks and benefits. An electronic trial information sheet and consent form will be created by EpiCore Centre (Appendix 3.2). The trial consent form will be signed by the patient either using a touch-interface (e.g.: iPad or similar device) or using a mouse to draw a signature (desktop computer), and witnessed by the study investigator or research assistant. The patient’s email address will be collected, and once the consent is signed, a copy will be emailed to the participant. In the event of technical difficulties, a participant without email access, or a participant that refuses electronic signing, paper copies of both the trial information sheet and consent forms will be available. An additional paper copies of the consent form, in that case, will be signed and given to the participant to take home.

Select providers (referring physicians / educators / dieticians and the study CDE nurse) will be approached and consented for semi-structured interviews to contribute their perspective on the use of isCGM. A specific information package and consent form for the qualitative sub-study (providers only – patients are covered by the full trial consent package) has been developed (Appendix 3.3).

Patients will be free to withdraw consent / withdraw from the study at any time, and will be given written instructions on termination of Libre 2 data sharing as part of the study information package (Appendix 4).

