10. STUDY OUTCOMES AND VARIABLES

Case report forms are provided in Appendix 5. These will be translated into electronic documents to be completed by participants via a password protected webportal (EpiCore).

Primary Outcome:

- Change in HbA1c at 12 weeks compared to baseline.

Secondary Outcomes:

- Feasibility of recruitment
 - Participant referral, screening, and randomization rates over time
 - Reasons for inclusion / exclusion of all participants referred.
- Change in scores at 6 and 12 weeks compared to baseline, on the patient-reported outcomes shown in Table 1, below.
- isCGM participants only – change in time-in-target range, coefficient of variation, and glucose management indicator at 12 weeks compared to baseline.

Table 1: Patient-Reported Outcomes

Outcome	Instrument	Number of items
Diabetes treatment satisfaction – Status score	Diabetes Treatment Satisfaction Questionnaire (DTSQs) ³⁷ (weeks 6 and 12)	8
Diabetes treatment satisfaction – Change score	Diabetes Treatment Satisfaction Questionnaire (DTSQc) (week 6 only)	
Self-management empowerment	Diabetes Empowerment Scale – Short Form (DES-SF) ³⁸ (weeks 6 and 12)	8
Diabetes-related distress	Problem Areas in Diabetes (PAID) Questionnaire ³⁹	20
Diet	UK Diabetes and Diet Questionnaire (UKDDQ) ⁴⁰ (weeks 6 and 12)	25
Physical activity	International Physical Activity Questionnaire (IPAQ) short form ^{41,42} (weeks 6 and 12)	7
Health status	Euroqol EQ-5D-5L (weeks 6 and 12)	5

* In addition to collection at baseline.

Safety outcomes at 12 weeks:

- Any adverse events (serious and non-serious) occurring from baseline to 12 weeks will be identified and tracked at the 12 week study visit by patient interview, and reviewed

by study investigators to determine whether clinically attributable to diabetes, diabetes management, or isCGM. isCGM issues (e.g.: skin reactions) will be specifically sought.

- Emergency department visits or hospital admission for any reason, identified from patient interview and from NetCare review.

Qualitative Outcomes: Semi-structured interviews will undergo thematic analysis using constant comparative methods. The starting point will be the participant and provider experience with isCGM or enhanced usual care, with a particular focus on barriers and enablers of effectiveness (see Appendix 6, interview guides). Semi-structured interviews will take place for participants after trial completion (from 12-24 weeks).

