18. ETHICAL CONSIDERATIONS

The study will be conducted in accordance with the Tri-Council Policy Statement.⁴⁴

Informed Consent of the Patient - Patients who meet all inclusion criteria and none of the exclusion criteria are deemed eligible. Before being enrolled into the clinical study, the patient must provide written consent to participate in the study after the nature, scope and possible consequences of the clinical study have been explained both orally and in writing.

Approval of the Study Protocol - Before the start of the study, the study protocol and the informed consent form used at the site and other appropriate documents must be submitted to and approved by the local Ethics Committee or Institutional Review Board (REB) and the appropriate regulatory authorities in accordance with local legal requirements.

Maintenance of Records - The Investigator agrees to obtain a correctly completed informed consent form for each patient included in the study. The investigator will maintain a personal list of patient numbers and patient names to enable records to be found at a later date. As per University policy data will be kept for 5 years from completion of the study. The REDCap database will be maintained for a period of 25 years from study completion.

Generation and Sharing of Remote Patient Data – isCGM data will automatically be shared with the clinic LibreView account to facilitate CDE nurse education and feedback, via internet-capable smart phones. Participants will be provided with written, graphic instructions on terminating data sharing. Data sharing will be terminated by study personnel during the 12 week in-person visit, or by special appointment if participants wish to terminate data sharing earlier and are unable to do so themselves.

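### Baseline questionnaires may be finished at home after open-label randomisation, so scores recorded with the arm known can enter the 6- and 12-week change scores

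*Combined protocol and SAP*

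**What the plan says.** - **One visit for everything.** Section 9 states that "eligible patients will attend a baseline visit to complete consent for participation and randomization, as well as completion of baseline measures". The text gives no order for these steps.
- **The arm is known at that visit.** In Section 6 a study team member starts the first sensor in the isCGM arm, sets up the app and will "link it to the study LibreView account during the baseline visit". On blinding, the same section says "Neither patients, investigators, nor statistical analysts will be blinded to treatment allocation".
- **Home completion is allowed.** Section 16, describing the REDCap patient portal, says "While the baseline and follow-up visits will still be in-person, participants may choose to finish filling in patient-reported outcomes from home". The sentence names the baseline visit and sets no deadline.
- **Baseline is the reference.** Section 10 defines the secondary outcome as "Change in scores at 6 and 12 weeks compared to baseline, on the patient-reported outcomes shown in Table 1". Section 14 analyses secondary outcomes in the same way as the primary one, by linear regression adjusted for age and sex.
- **Dates are recorded.** Each questionnaire in Appendix 5.4 has a completion date and Appendix 5.1 has a randomisation date. No rule compares them, and no time of day is listed.

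**The concern.** In an open-label trial a self-reported baseline is a clean reference only if it is recorded before the participant knows the arm. Here a participant can go home with a sensor on the arm, or knowing that none will be given, and only then finish the baseline questionnaires.

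If that knowledge moves the answers, the arms differ at baseline for a reason other than chance, and the difference is subtracted from the follow-up score. The direction cannot be predicted: getting the device could raise satisfaction, and seeing readings could raise distress. Patient self-management is named in the study hypothesis (Section 3), so these comparisons will be read with interest even though Section 14 calls secondary outcomes hypothesis-generating.

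**Working it through.** **1. Can a baseline form follow allocation?** Section 9 says "The trial consent form will be signed by the patient", and Section 18 says "Before being enrolled into the clinical study, the patient must provide written consent to participate in the study". Consent is thus given at the baseline visit, so filling in the forms at home beforehand is not a natural reading. Randomisation also takes place at that visit. A form finished at home after it therefore follows allocation, whatever the order of steps within the visit. Figure 1 was not available in the text reviewed. It may set an in-visit order, but it would still have to be reconciled with the Section 16 permission.

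**2. Which forms are exposed?** Six instruments have a baseline form in Appendix 5.4. Six is a ceiling, because finishing at home implies that some forms are done at the visit.

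| Instrument | Period asked about | Exposure if finished soon after the visit |
|---|---|---|
| PAID | current problems | yes |
| EQ-5D-5L | today | possible; general health items |
| DTSQs | past few weeks, but items on current treatment | mixed |
| DES-SF | general beliefs | possible |
| IPAQ | last 7 days | small |
| UKDDQ | last month | very small |

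DTSQc (week 6 only) has no baseline form. HbA1c, blood pressure, weight and waist are measured, not self-reported.

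**3. How a shift passes through.** Let p be the share of baseline forms finished after allocation and d the mean shift in those forms, by arm (1 = isCGM, 0 = control). Then

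bias in the difference in mean change = -(p1 × d1 - p0 × d0).

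The documents give none of these four quantities. For an illustration I **assume** a shift in one arm only, p = 10-50% and d = 0.1-0.5 SD.

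For precision I use the plan's 40 completers per arm. That figure reproduces: 2 × (1.960 + 0.842)² × 0.78² / 0.5² = 38.2, so 39 by the normal formula; the t-based calculation gives 39.2, so 40; and 80 / (1 - 0.20) = 100.

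At an assumed baseline/follow-up correlation r = 0.5, SE of the change difference = √(2(1 - 0.5)) × √(2/40) = 0.224 SD.

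| p | d (SD) | Size of bias (SD) | Bias / SE | Two-sided error at nominal 5% |
|---|---|---|---|---|
| 0.10 | 0.1 | 0.01 | 0.04 | 5.0% |
| 0.25 | 0.3 | 0.075 | 0.34 | 6.3% |
| 0.50 | 0.5 | 0.25 | 1.12 | 20% |

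This applies to a form with no look-back window. If only the part of the window after allocation can shift, a form one day late has 1/7 of that bias for IPAQ (0.01/7 to 0.25/7 = 0.001-0.036 SD) and 1/30 for UKDDQ (0.0003-0.008 SD).

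**4. Would adjusting for the baseline score solve it?** No. The late score is no longer a pre-randomisation covariate. The bias shrinks to about r × 0.075 in the middle case, that is 0.02, 0.04 and 0.05 SD at r = 0.3, 0.5 and 0.7. A simulation of the middle case (6,000 trials per correlation, true effect zero, 40 per arm; Monte Carlo error about 0.003) agrees with the algebra:

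| Analysis (arm, age, sex) | r = 0.3 | r = 0.5 | r = 0.7 |
|---|---|---|---|
| Change score | -0.072 | -0.072 | -0.073 |
| Follow-up score, late baseline as covariate | -0.023 | -0.034 | -0.051 |
| Follow-up score, no baseline | -0.002 | 0.003 | -0.001 |

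The simulation only checks the algebra. It says nothing about the size of the problem in this trial.

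**The case against.** The best defence has four parts.

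1. **Section 9 can be read as placing completion of baseline measures at the visit.** On that reading Section 16 merely describes a portal that serves all time points. This is fair as far as it goes: the two sections are loose against each other, and there is no settled plan to collect baseline scores late. But Section 16 names the baseline visit and gives an express permission, so staff who follow it would be within the protocol.
2. **The exposure is narrow.** UKDDQ and IPAQ are barely touched, DES-SF asks about general beliefs, and most EQ-5D-5L items are unlikely to move with device allocation. That leaves mainly PAID and some DTSQs items, and DTSQc gives a satisfaction comparison that needs no baseline. This stands as a limit on size. It does not help PAID.
3. **Safeguards partly exist.** The recorded dates identify forms finished on a later day, though not those finished on the same day after allocation. Section 14 also mentions follow-up values at 6 and 12 weeks, which might already mean a comparison without baseline, but the wording is ambiguous.
4. **The outcomes are secondary and the size is unknown.** Both are true. The upper illustrative value needs half of one arm's forms to be late and a shift of half an SD, and no document supports either. A hypothesis-generating label, however, bears on error rates and does not correct a biased reference score.

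**Conclusion.** The concern holds. Followed as written, the plan lets some baseline patient-reported scores be recorded after allocation is known and then used as the reference for change. The text shows that this can happen, not that it will or how often.

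The size cannot be determined from the documents. The range of 0.01-0.25 SD (0.04-1.1 standard errors at 40 per arm) rests wholly on the assumed shares, shifts, one-arm effect and correlation of 0.5. The primary outcome, the sample size and the physical measures are unaffected. It should be changed because prevention is cheap and a contaminated baseline cannot be collected again. It is not a threat to the main result. Confidence is medium, given the unknown frequency and the unseen Figure 1.

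**What to change.** **Change.** In Sections 9 and 16, require the baseline patient-reported forms to be completed and time-stamped in REDCap at the baseline visit, after written consent and before the allocation is released. Limit home completion to weeks 6 and 12. Week 6 needs it, because eligibility is built on two attendances ("Able to attend two in-person study visits"). Check that Figure 1 agrees.

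**Participants already enrolled, and any form still late.** Keep the form. Flag it by comparing its completion date with the randomisation date, and by the time stamp for same-day forms. Report the number by arm. In Section 14, state plainly that a sensitivity comparison of the 6- and 12-week scores will be made without the baseline score. Label any analysis that leaves out late forms as exploratory, since lateness may itself depend on arm.

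**Cost.** A sentence each in Sections 9 and 16, a clarification in Section 14 and a time stamp; no extra patients.

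The baseline visit becomes longer for those who would have finished at home. Table 1 gives 8 + 8 + 20 + 25 + 7 + 5 = 73 items. Appendix 5.4 also prints two further UKDDQ questions and the EQ-5D visual scale, making 76. At an assumed 10-20 seconds per item, the whole set takes about 13-25 minutes, and longer if the activity recall is slow. A rushed visit could leave forms missing, and a missing baseline drops that participant from a change-score analysis, so adequate time must be scheduled.

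The sensitivity comparison has SE √(2/40) = 0.224 SD. The change score has 0.265, 0.224 and 0.173 SD at r = 0.3, 0.5 and 0.7. The sensitivity SE is therefore 15% smaller, equal and 29% larger respectively.

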17. FEASIBILITY AND LIMITATIONS

Feasibility of the trial:

The trial is small, features a short follow-up period, and deploys existing (licensed and marketed) technologies, which have demonstrated benefits in other sub-populations of adults with diabetes. Trial needs are relatively straightforward.

The EPICORE Centre has extensive experience in clinical trials, supporting numerous investigators, with a lengthy list of completed and on-going projects (<https://www.epicore.ualberta.ca/home/>). They will provide data base and analysis support.

The team of study investigators is small, but collectively covers formal expertise in clinical epidemiology and sophisticated statistical analyses, diabetes care from both specialist and primary care lenses, and significant experience with clinical trials and qualitative / mixed methods evaluations in the context of primary care quality improvement.⁴³ The more experience study investigators are well established in local and regional clinical care organizations, and we expect to leverage their interpersonal contacts to enable participant recruitment.

Limitations and Design Issues:

- *Episodic and short-term use of isCGM.* We have designed the intervention to test the effectiveness of *episodic* isCGM, recognizing that, in the current cost and insurance coverage environment, many patients will only be able to afford isCGM on an episodic basis. Our results may not generalize to continuous or longer duration use of isCGM, or to a longer, more continuous CDE education and feedback.
- *Enhanced usual care control group does not formally feature support for capillary blood glucose monitoring.* Our control group is usual care enhanced with CDE education and feedback, which may include CDE recommendation that patients undergo self-monitoring of blood glucose with capillary blood glucose monitors, but not on a protocolized or formal basis. There is variable evidence that capillary blood glucose monitoring can improve glycemic control in this population, but a formal test of isCGM compared to capillary blood glucose monitoring is beyond the scope of the present trial.
- *Limited trial period of 12 weeks.* There is the possibility that insufficient time may have elapsed by the 12 week study HbA1c to see the effect of the intervention, since the 12 week HbA1c may be influenced by blood glucose exposure early in the trial period, before isCGM-based changes are made. Additionally, the 12 month outcome will not be able to speak to the sustainability of any isCGM benefits detected. We have designed a post-trial observational follow-up to address the longer term outcomes of episodic isCGM, recognizing that the follow analysis will no longer benefit from the expected confounder balance of randomization, as participants who consent to data linkage and who have HbA1c measurements post-trial will represent a non-random subset of those initially randomized.
- *Limited support to titrate anti-hyperglycemic medications.* The presumptive mechanism for any improvement in glycemic control is improved diet and lifestyle modification in adults randomized to isCGM. An alternative mechanism may be more rapid medication titration based on isCGM data, instead of HbA1c measurements, which are recommended at intervals no less than 90 days. While the

CDE algorithm (currently under development) may have a role for CDE-to-provider suggestions for medication changes, the intervention is not intended to provide further support or practice change related to provider prescribing (e.g.: decision support, alternate prescribers, provider training).

- *Sample size still has a 20% risk of type 2 error* – Our study is powered to detect a 0.5% difference in HbA1c at a power of 80%. The type 2 error rate (failure to detect a difference on such a difference truly exists) is still 20%, though may be slightly lower if loss-to-follow-up is minimized and recruitment approaches the full 100 participants.

